[figure not shown]

NON-INTERVENTIONAL (NI) STUDY PROTOCOL

Study Information

Title	Evaluation of satisfaction with rimegepant and triptans utilizing	
	Migraine Buddy retrospective data	
Protocol number	C4951073	
Protocol version	V1.0	
identifier		
Date	04 June 2024	
Active substance	Analgesics, calcitonin gene-related peptide (CGRP) antagonists. ATC code: N02CD06	
Medicinal product	Rimegepant (Nurtec 75mg ODT)	
Research question and objectives	Primary objective: This study aims to assess the holistic benefit of rimegepant as compared to triptans, particularly in relation to patients' satisfaction with regards to medication efficacy, tolerability and migraine-induced cognitive impact.	
	Research questions:	
	1. How does satisfaction with pain intensity compare between adults diagnosed with migraine who are using Nurtec or triptans as an acute treatment for migraine?	
	2. How does satisfaction with attack duration compare between adults diagnosed with migraine who are using Nurtec or triptans as an acute treatment for migraine?	
	3. How does satisfaction with speed of action compare between adults diagnosed with migraine who are using Nurtec or triptans as an acute treatment for migraine?	
	4. How does satisfaction with migraine-induced cognitive impact compare between adults diagnosed with migraine who are using Nurtec or triptans as an acute treatment for migraine?	
	5. How does satisfaction with tolerability compare between adults diagnosed with migraine who are using Nurtec or triptans as an acute treatment for migraine?	
	6. How does satisfaction with relief of other symptoms compare between adults diagnosed with migraine who are using	

This document contains confidential information belonging to Pfizer. Except as otherwise agreed to in writing, by accepting or reviewing this document, you agree to hold this information in confidence and not copy or disclose it to others (except where required by applicable law) or use it for unauthorized purposes. In the event of any actual or suspected breach of this obligation, Pfizer must be promptly notified.

2. LIST OF ABBREVIATIONS

Abbreviation	Definition
ADH	Aptar Digital Health
AE	Adverse Event
CGRP	Calcitonin Gene-related Peptide
CM	Chronic Migraine
CV	Cardiovascular
EM	Episodic Migraine
EMA	European Medicines Agency
НСР	Healthcare Professional
HIPPA	Health Insurance Portability and Accountability Act
HT	Hydroxytryptamine
ICJME	International Committee of Medical Journal Editors
IRB	Institutional Review Board
ISPOR	International Society for Pharmacoeconomics and Outcomes Research
MHD	Monthly Headache Day
MMD	Monthly Migraine Day
NRDL	National Reimbursement Drugs List
ODT	Orally Disintegrating Tablet
QoL	Quality of Life
RCT	Randomized control trial
SD	Standard Deviation

Abbreviation	Definition
US	United States of America

4. AMENDMENTS AND UPDATES

None.

5. MILESTONES

Milestone	Planned Date
Initiation of data analysis	09 June 2024
Completion of data analysis	10 June 2024
Abstract	14 June 2024

6. RATIONALE AND BACKGROUND

Migraine is a common, often disabling neurologic disease characterized by recurrent attacks of head pain that are typically unilateral, throbbing, and associated with a range of symptoms that may include photophobia, phonophobia, nausea, and vomiting.¹⁻³ Migraine can be classified as episodic or chronic based on the frequency of the migraine or headache: episodic migraine (EM) is characterized by one to 14 monthly headache days (MHDs) or monthly migraine days (MMDs), while chronic migraine (CM) is characterized by 15 or more MHDs for at least three months, with at least eight days a month on which the headaches and associated symptoms meet diagnostic criteria for migraine.^{1,3,4} Migraine is a clinically complex disorder, and in addition to its direct clinical burden, patients experience a greater number of comorbidities compared to those without migraine.⁵

While treatment goals vary by region, guidelines from both the US and France (the most recently published treatment goals in Europe) for acute migraine treatment suggest these are rapid and sustained freedom from pain, improvement in other migraine symptoms, and minimal or no adverse events (AEs).^{6,7} There is significant need for effective and tolerable treatments for migraine sufferers, especially those who experience at least four migraine days per month. In these patients, preventive treatment is recommended to reduce migraine-related disability and the overuse of acute therapies and rescue medication.⁶ Both US and European guidelines note the importance of reduced attack frequency, reduction or maintenance (no escalation) of acute treatment use, and an improvement in quality of life (QoL).^{6,7} Current migraine treatments leave millions of people who have migraine with unmet needs due to lack of and/or insufficient efficacy, AEs, and contraindications.^{8,9}

Treatment strategies aim to abort episodic symptoms and reduce the frequency of attacks, with "triptans" (5-hydroxytryptamine [5-HT]1b/1d receptor agonists) being the most commonly used prescription medications for acute treatment. However, their effectiveness is not universal, and due to vasoconstrictive effects, they are contraindicated in patients with known cardiovascular disease (CV). Recent advancements have introduced 2 novel classes of acute migraine medications: selective 5-HT1F agonists ("ditans") and CGRP antagonists ("gepants"), with the U.S. Food and Drug Administration approving Lasmiditan, Ubrogepant, and rimegepant for the acute treatment of migraine in adults.

Rimegepant (VYDURA®/NURTEC® ODT), a next-generation, small molecule oral selective and potent calcitonin gene-related peptide (CGRP) receptor antagonist, is the first and only migraine treatment approved for both the acute treatment of migraine with or without aura in adults and for the preventive treatment of EM in adults who have at least four

migraine attacks per month. Prior to rimegepant, there was no single medication proven to be safe and effective for both acute and preventive treatment of migraine. Rimegepant was approved in the US for the acute treatment of migraine in February 2020, and for preventive treatment of episodic migraine in adults who have at least 4 migraine attacks per month in May 2021. It was approved by the EMA for both indications in April 2022.

There is a lack of published studies comparing directly triptans which are the most commonly used prescription medications for acute treatment with rimegepant. Existing indirect comparisons between the randomized controlled trials (RCTs) of rimegepant and triptans are confounded by high levels of heterogeneity leading to biased results.

This study will utilize retrospective data collected with the Migraine Buddy Mobile application to evaluate satisfaction of treatment with rimegepant and triptans. The primary motivation for the study is to generate evidence to support a submission to the National Reimbursement Drugs List (NRDL) in China, but it is anticipated that results will also be of relevance to health care providers and payers outside of China.

7. RESEARCH QUESTION AND OBJECTIVES

Primary objective: The objective of this study is to assess the holistic benefit of rimegepant as compared to triptans, particularly in relation to patients' satisfaction with regards to medication efficacy, tolerability, and migraine-induced cognitive impact.

Research questions:

- 1. How does satisfaction with pain intensity compare between adults diagnosed with migraine who are using Nurtec or triptans as an acute treatment for migraine?
- 2. How does satisfaction with attack duration compare between adults diagnosed with migraine who are using Nurtec or triptans as an acute treatment for migraine?
- 3. How does satisfaction with speed of action compare between adults diagnosed with migraine who are using Nurtec or triptans as an acute treatment for migraine?
- 4. How does satisfaction with migraine-induced cognitive impact compare between adults diagnosed with migraine who are using Nurtec or triptans as an acute treatment for migraine?
- 5. How does satisfaction with tolerability compare between adults diagnosed with migraine who are using Nurtec or triptans as an acute treatment for migraine?
- 6. How does satisfaction with relief of other symptoms compare between adults diagnosed with migraine who are using Nurtec or triptans as an acute treatment for migraine?

7. How do clinical characteristics (for eg, migraine severity, current migraine prophylactic treatment use) impact patients' satisfaction with regards to medication efficacy, tolerability and migraine-induced cognitive impact in those who are using Nurtee or triptans as an acute treatment for migraine.

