8.3. Variables

For this retrospective study, the only variables collected are the self-reported satisfaction of Migraine Buddy users via a questionnaire accessible from the home screen of the app. Satisfaction with Nurtec or triptans was asked in relation to several dimensions: pain intensity, attack duration, speed of action, cognitive impact of Migraine, tolerability, and other symptoms.

Variable	Role
Current acute treatment (s)	Patient treatments
Current prevention treatment (s)	Patient treatments
Monthly migraine Days	Clinical Characteristics
Satisfaction with treating pain	Outcome
Satisfaction with reducing attack duration	Outcome
Satisfaction with speed of pain relief	Outcome
Satisfaction with reduction of migraine-	Outcome

Variable	Role
cognitive impact	
Satisfaction with tolerability	Outcome
Satisfaction with relief of other symptoms	Outcome

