8.7. Data Analysis

The study analysis population will include patients who received Nurtec and/or triptans as an acute treatment currently for their migraine.

The feasibility of subgroup analyses will be explored (eg, by migraine severity, currently using prophylactic treatment). Feasibility will evaluate if there is sufficient sample size for meaningful comparisons. All outcomes will remain blinded for the feasibility assessment.

The mean, standard deviation (SD), median, 25th and 75th percentiles and minimum and maximum values will be reported for numeric variables, whilst relative frequencies and percentages will be reported for categorical variables.

To compare the outcome measures (Section 7) between adults diagnosed with migraine who are using either Nurtec or triptans as an acute treatment for migraine, appropriate tests (eg, t-test, chi-square test) will be used based on the distribution of the measure. The alpha level will be 0.05, 2-sided. No adjustments for multiple comparisons will be made.

The real-world nature of the Migraine Buddy app means variables may contain different proportions of missing data. We would expect the non-missing observations (the 'base') of patients to vary from variable to variable. The base relevant to each analysis will be reported in any data tables provided. This study will use a 'complete case analysis' approach to handle missing values, ie, there will be no imputation of missing data. Where missing values are found in a particular variable, any patients with missing values will be removed from all pieces of analysis where that variable is used. However, patients removed from one piece of analysis are still eligible for inclusion in other analyses.¹¹

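### Research question 7 has no committed analysis that estimates the effect of a clinical characteristic, and migraine severity is not tied to any listed variable

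*Combined protocol and SAP*

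**What the plan says.** Section 7 lists seven research questions. The first six compare Nurtec with triptans on six satisfaction dimensions. The seventh is of a different kind: "How do clinical characteristics (for eg, migraine severity, current migraine prophylactic treatment use) impact" satisfaction in people using either drug.

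Section 8.7 is the whole analysis plan. On characteristics it says: "The feasibility of subgroup analyses will be explored (eg, by migraine severity, currently using prophylactic treatment"). The criterion is "Feasibility will evaluate if there is sufficient sample size for meaningful comparisons", with no number attached. The only tests described are for comparing adults "who are using either Nurtec or triptans as an acute treatment for migraine, appropriate tests (eg, t-test, chi-square test) will be used". It adds "The alpha level will be 0.05, 2-sided" and "No adjustments for multiple comparisons will be made".

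The Section 8.3 table gives the role of clinical characteristic to one variable, "Monthly migraine Days". It also lists current preventive treatment, under patient treatments. It has no severity variable. The sentence above the table says that "the only variables collected are the self-reported satisfaction of Migraine Buddy users", which does not agree with the table.

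**The concern.** A question about how a characteristic relates to satisfaction needs an estimate of that relation: a contrast between levels of the characteristic, or a slope, within each drug. If the question is whether the drug comparison depends on the characteristic, it needs an interaction. Section 8.7 promises neither. It offers subgroup analyses that may or may not be run, and the only contrast it describes is drug against drug.

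Two things are at stake. First, the seventh question could go unanswered without any departure from the plan. Second, if subgroups are run with the tests that are named, the output would be a set of p-values by stratum. A drug difference that is significant in preventive users and not in non-users invites the reading that preventive use matters, and that pattern arises often when nothing differs. Section 6 says the evidence is meant to support a reimbursement submission, so a chance subgroup pattern could carry weight.

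Severity adds a separate difficulty. It is named in both Section 7 and Section 8.7, but nothing says which variable measures it.

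**Working it through.** **Text check.**

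| Element | What is stated | What is absent |
|---|---|---|
| Question 7 (Section 7) | Effect of characteristics on satisfaction; severity and preventive use as examples | A definition of severity |
| Tests (Section 8.7) | t-test or chi-square as examples, Nurtec against triptans | Any contrast between levels of a characteristic; any regression or interaction |
| Subgroups (Section 8.7) | Feasibility to be explored | A commitment, a size threshold, the form of the comparison |
| Variables (Section 8.3 table) | Monthly migraine days; current preventive treatment | Severity, or a statement that monthly days stand for it |

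Section 6 uses monthly days to classify migraine by frequency, so the protocol's own use of the measure is not one of severity.

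**Illustration of stratum-by-stratum testing.** The plan states no power, effect size, satisfaction rate or subgroup split, so there is no figure of its own to reproduce.

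- From Section 8.5: about 700 Nurtec and 800 triptan ratings. From Section 8.7: alpha 0.05, two-sided.
- Assumed: independent groups; 60% satisfied in the group of 700; 60% minus d in the group of 800; the same d in both strata; splits of 50:50 and 80:20.

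Formulas, for a stratum with n1 and n2 ratings:

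- SE = √[p1(1−p1)/n1 + p2(1−p2)/n2]
- power = Φ(d/SE − 1.960) + Φ(−d/SE − 1.960)
- P(exactly one stratum significant) = PA(1−PB) + PB(1−PA)

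Worked case, d = 7.2 points, 50:50 split, 350 and 400 per stratum: SE = √(0.600×0.400/350 + 0.528×0.472/400) = 0.0362; d/SE = 1.990; power 0.512 in each stratum; P = 2×0.512×0.488 = 0.50. With all 700 and 800 the same d gives 80% power.

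Same d, 80:20 split: the powers are 0.711 (560 and 640) and 0.242 (140 and 160), so P = 0.711×0.758 + 0.242×0.289 = 0.61.

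| True difference, same in both strata | 50:50, power in each | 50:50, exactly one significant | 80:20, powers | 80:20, exactly one significant |
|---|---|---|---|---|
| 3 points | 0.13 | 23% | 0.18, 0.08 | 24% |
| 5 points | 0.28 | 41% | 0.42, 0.14 | 44% |
| 7.2 points | 0.51 | 50% | 0.71, 0.24 | 61% |
| 10 points | 0.79 | 33% | 0.94, 0.42 | 57% |
| 15 points | 0.99 | 3% | 1.00, 0.75 | 25% |

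In every row the characteristic modifies nothing.

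**Precision of a direct interaction estimate.** On a standardised scale, SE = √(sum of 1/n over the four cells), and the detectable difference at 80% power is (1.960 + 0.842)×SE. Again assuming independent groups:

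- Overall drug difference, 700 and 800: 0.145 SD.
- Interaction, 50:50: √(2/350 + 2/400) = 0.1035, times 2.802 = 0.290 SD.
- Interaction, 80:20: √(1/560 + 1/640 + 1/140 + 1/160) = 0.1294, times 2.802 = 0.362 SD.

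The interaction must be at least twice the detectable overall difference to be found with the same power.

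**The case against.** A reader might infer that question 7 cannot be answered at all. The documents do not support that. Current preventive treatment is in the Section 8.3 table and is one of the question's own two examples. Monthly migraine days is also listed and may be the intended stand-in for severity. The examples are an open list, and nothing ranks severity first.

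A reader might also infer that the plan prescribes drug tests within each stratum. It does not: Section 8.7 leaves the form of the subgroup analysis open, and its tests are given only as examples. The same tests could compare preventive users with non-users within one drug, which would be a direct, unadjusted answer if the question is read as one of association and not of effect modification. Nor does anything in the text say that stratum results would be read against each other.

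The size of the risk depends on assumed inputs. For an even split, 50% is the maximum, and the chance falls to 3% at 15 points. An interaction test would often be inconclusive too. Finally, Section 8.1 makes the Nurtec–triptan comparison the primary endpoint, and the feasibility step is blinded to outcome, so questions 1 to 6 are untouched.

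All of this stands as a limit on the claim. It does not supply an analysis: a comparison that the plan could have named is not one that it commits to, and severity remains undefined.

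**Conclusion.** The point holds in a limited form. Followed as written, Section 8.7 need not produce an estimate of any characteristic's effect on satisfaction, and severity as named in Sections 7 and 8.7 has no variable behind it. For monthly migraine days and preventive use the data are listed and the question can be addressed.

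The inferential risk is conditional on the drug-versus-drug tests being used by stratum, which is an inference from the tests named. Under that condition a misleading split in significance occurs in 3% to 50% of studies for two equal strata and 24% to 61% for an 80:20 split, over true differences of 3 to 15 points. These ranges assume independent groups and 60% satisfied on one drug. Section 8.5 says the groups may overlap, which would change the figures by an amount that the documents do not allow to be calculated. They apply to one outcome at a time; nothing supports assuming the same difference on all six dimensions.

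**What to change.** For each satisfaction dimension, fit one model on all ratings, with clustering by user because the same person may rate both drugs. Include drug, monthly migraine days (continuous), current preventive use (yes/no) and the drug-by-characteristic interactions. Answer question 7 from the characteristic estimates within each drug and from the interaction estimates, each with a 95% CI and labelled exploratory. This serves both the association reading and the effect-modification reading. If subgroup tables are kept, state the minimum size that makes one feasible, and do not draw conclusions from p-values by stratum.

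In the text, replace migraine severity with monthly migraine days in Sections 7 and 8.7, or add a diary severity variable to Section 8.3 if one is held. Reconcile the Section 8.3 sentence on what is collected with its table. Do not present a cut at 15 migraine days as the definition of chronic migraine in Section 6: that definition uses 15 or more headache days for at least three months, with at least eight days meeting migraine criteria.

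The cost is one regression per outcome on variables already in the table, plus wording. The interaction intervals will be wide, and the report should say so.

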8. RESEARCH METHODS

8.1. Study Design

This is a retrospective analysis of cross-sectional data collected in the Migraine Buddy app between 20 October 2023 and 20 May 2024 from US users.

Migraine Buddy users reporting current use of an acute treatment for their migraine attacks completed a survey assessing their satisfaction with the acute migraine drugs being used. Data from users reporting use of Nurtec and/or a triptan (and Rizatriptan in particular) will be extracted for analysis.

The primary endpoint is the level of satisfaction on several dimensions of migraine characteristics. Survey questions ask specifically about satisfaction with Nurtec or the triptan. The level of satisfaction with Nurtec will be compared to the level of satisfaction with triptans.

The strength of this design is the real-life setting of the data collected. Users were using the Migraine Buddy app for tracking their migraines in real life.

8.2.1. Inclusion Criteria

Patients who used Nurtec and/or triptans as an acute treatment for migraine, with or without a background of preventive treatment (anti-CGRP, Botox or oral migraine preventive medications).

Patients must meet all of the following inclusion criteria to be eligible for the study:

- 1. Male or female participants with migraine
- 2. Having consented to the anonymous use of their data for research
- 3. Currently using Nurtec and/or triptans to treat migraine attacks

8.2.2. Exclusion Criteria

Patients meeting any of the following criteria will not be included in the study:

1. Users who did not report using either medication for which they complete the survey within 60 days prior to the survey.

8.3. Variables

For this retrospective study, the only variables collected are the self-reported satisfaction of Migraine Buddy users via a questionnaire accessible from the home screen of the app. Satisfaction with Nurtec or triptans was asked in relation to several dimensions: pain intensity, attack duration, speed of action, cognitive impact of Migraine, tolerability, and other symptoms.

Variable	Role
Current acute treatment (s)	Patient treatments
Current prevention treatment (s)	Patient treatments
Monthly migraine Days	Clinical Characteristics
Satisfaction with treating pain	Outcome
Satisfaction with reducing attack duration	Outcome
Satisfaction with speed of pain relief	Outcome
Satisfaction with reduction of migraine-	Outcome

Variable	Role
cognitive impact	
Satisfaction with tolerability	Outcome
Satisfaction with relief of other symptoms	Outcome

8.4. Data Sources

Data source is the Migraine Buddy app responses to questions in the satisfaction survey. The Migraine buddy app and its database is owned by ADH, after the acquisition of Healint. The satisfaction levels refer to the medication in general. They are not tied to specific attacks. To avoid a recall bias, data from users answering the survey more than 60 days after the last time they reported using Nurtec or a triptan will be discarded.

This questionnaire asked the level of satisfaction with their treatment on a 7-levels Lickert scale. (1 = extremely dissatisfied to 7 = extremely satisfied). Based on their responses, the respondents will be stratified into those who were dissatisfied (reporting 1 = extremely dissatisfied to 3 = somewhat dissatisfied), neutral (4=neither dissatisfied nor satisfied) or satisfied (reporting 5 = somewhat satisfied to 7 = extremely satisfied) with the treatment. Data will be reported for the overall cohort, no individual data will be shared.

